#### **8.2.5. Clinical Safety Laboratory Assessments**

See [Appendix 2](#) for the list of clinical safety laboratory tests to be performed and the **SoA** for the timing and frequency.

The investigator must review the laboratory report, document this review, and record any clinically relevant changes occurring during the study in the AE section of the CRF. Clinically significant abnormal laboratory findings are those which are not associated with the underlying disease, unless judged by the investigator to be more severe than expected for the participant's condition.

All laboratory tests with values considered clinically significantly abnormal during participation in the study up to the time of the final planned follow-up visit after the last dose of study intervention should be repeated until the values return to normal or baseline or are no longer considered clinically significant by the investigator or medical monitor.

If such values do not return to normal/baseline within a period of time judged reasonable by the investigator, the etiology should be identified and the sponsor notified.

All protocol-required laboratory assessments, as defined in [Appendix 2](#), must be conducted in accordance with the laboratory manual and the **SoA**.

If laboratory values from non-protocol-specified laboratory assessments performed at the institution's local laboratory require a change in participant management or are considered clinically significant by the investigator (eg, SAE or AE or dose modification), then the results must be recorded in the CRF.

### **8.2.6. Pregnancy Testing**

Pregnancy tests may be urine or serum tests, but must have a sensitivity of at least 25 mIU/mL. Pregnancy tests will be performed in WOCBP at the times listed in the [SoA](#). Urine pregnancy tests will be provided by the central lab. Following a negative pregnancy test result at screening, appropriate contraception must be commenced and a second negative pregnancy test result will be required at the baseline visit prior to the participant's receiving the PF-06946860. Pregnancy tests will also be done whenever 1 menstrual cycle is missed during the active treatment period (or when potential pregnancy is otherwise suspected) and at the end of the study. Pregnancy tests may also be repeated if requested by institutional review boards (IRBs)/ethics committees (ECs) or if required by local regulations. If a urine test cannot be confirmed as negative (eg, an ambiguous result), a serum pregnancy test is required. In such cases, the participant must be excluded if the serum pregnancy result is positive.

## **8.3. Adverse Events and Serious Adverse Events**

The definitions of an AE and an SAE can be found in [Appendix 3](#).

AEs will be reported by the participant (or, when appropriate, by a caregiver, surrogate, or the participant's legally authorized representative). AEs will be assessed based on CTCAE 5.0.

The investigator and any qualified designees are responsible for detecting, documenting, and recording events that meet the definition of an AE or SAE and remain responsible to pursue and obtain adequate information both to determine the outcome and to assess whether it meets the criteria for classification as an SAE or that caused the participant to discontinue the study (see [Section 7](#)).

In addition, the investigator may be requested by Pfizer Safety to obtain specific follow-up information in an expedited fashion.

### **8.3.1. Time Period and Frequency for Collecting AE and SAE Information**

The time period for actively eliciting and collecting AEs and SAEs ("active collection period") for each participant begins from the time the participant provides informed consent, which is obtained before the participant's participation in the study (ie, before undergoing any study-related procedure and/or receiving investigational product), through and including a minimum of up to the time of the final planned follow-up visit, after the last administration of the investigational product.

Follow-up by the investigator continues throughout and after the active collection period and until the event or its sequelae resolve or stabilize at a level acceptable to the investigator, and Pfizer concurs with that assessment.

For participants who are screen failures, the active collection period ends when screen failure status is determined.

If the participant withdraws from the study and also withdraws consent for the collection of future information, the active collection period ends when consent is withdrawn.

If a participant definitively discontinues or temporarily discontinues study intervention because of an AE or SAE, the AE or SAE must be recorded on the CRF and the SAE reported using the CT SAE Report Form.

Investigators are not obligated to actively seek AEs or SAEs after conclusion of the study participation. However, if the investigator learns of any SAE, including a death, at any time after a participant has been discharged from the study, and he/she considers the event to be reasonably related to the study intervention, the investigator must promptly report the SAE to Pfizer using the CT SAE Report Forms.

### **8.3.1.1. Reporting SAEs to Pfizer Safety**

All SAEs occurring in a participant during the active collection period are reported to Pfizer Safety on the CT SAE Report Form immediately and under no circumstance should this exceed 24 hours, as indicated in [Appendix 3](#). The investigator will submit any updated SAE data to the sponsor within 24 hours of it being available.

If a participant begins a new anticancer therapy, SAEs occurring during the above-indicated active collection period must still be reported to Pfizer Safety irrespective of any intervening treatment. Note that a switch to a commercially available version of the study intervention is considered as a new anticancer therapy for the purposes of SAE reporting.

### **8.3.1.2. Recording Nonserious AEs and SAEs on the CRF**

All nonserious AEs and SAEs occurring in a participant during the active collection period, which begins after obtaining informed consent as described in [Section 8.3.1](#), will be recorded on the AE section of the CRF.

The investigator is to record on the CRF all directly observed and all spontaneously reported AEs and SAEs reported by the participant.

If a participant begins a new anticancer therapy, the recording period for nonserious AEs ends at the time the new treatment is started; however, SAEs must continue to be recorded on the CRF during the above-indicated active collection period. Note that a switch to a commercially available version of the study intervention is considered as a new anticancer therapy for the purposes of SAE reporting.

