#### Type of Participant and Disease Characteristics:

2. Participants who are willing and able to comply with all scheduled visits, treatment plan, laboratory tests, lifestyle considerations, and other study procedures.
3. Documented histologic or cytologic diagnosis of advanced metastatic NSCLC, advanced/unresectable pancreatic cancer, or metastatic colorectal cancer by American Joint Committee on Cancer (AJCC) criteria
4. Cachexia, defined using Fearon's criteria:
  - Body Mass Index (BMI)  $<20 \text{ kg/m}^2$  with involuntary weight loss of  $>2\%$  within 6 months prior to screening; or
  - Involuntary weight loss of  $>5\%$  within 6 months prior to screening irrespective of BMI; or

If medical record documentation is unavailable, patient's report will suffice to estimate involuntary body weight loss.
5. Serum GDF-15 levels of  $\geq \text{CCI}$  (as measured using the Investigational Use Only Roche Elecsys GDF-15 assay) at screening.

6. Participants considered eligible for systemic anti-cancer treatment/therapy at the time of screening, who:
  - Are diagnosed with advanced metastatic NSCLC who will be treated with:
    - A platinum + pemetrexed  $\pm$  pembrolizumab; or
    - A platinum + nab paclitaxel or paclitaxel  $\pm$  pembrolizumab; or
    - Pembrolizumab alone.
  - Are diagnosed with advanced/unresectable pancreatic cancer who will be treated with:
    - FOLFIRINOX; or
    - Nab-Paclitaxel + Gemcitabine;
    - Gemcitabine.
  - Are diagnosed with metastatic colorectal cancer who will be treated with:
    - FOLFOX +/- Biologic (Bevacizumab or Cetuximab/Panitumumab); or
    - FOLFIRI +/- Biologic (Bevacizumab or Cetuximab/Panitumumab); or
    - FOLFOXIRI +/- Biologic (Bevacizumab or Cetuximab/Panitumumab); or
    - Pembrolizumab for MSI-H.
  - Will be entering the study at the first or second cycle of their current course of anti-cancer treatment/therapy.

Note: Other therapies can be considered upon discussion with the Pfizer medical monitor.

7. Adequate liver function as evidenced by liver enzymes, including:

- Total serum bilirubin  $\leq$ 1.5 x upper limit of normal (ULN) unless the participant has documented Gilbert syndrome;
- Aspartate and Alanine aminotransferase (AST and ALT)  $\leq$ 2.5 x ULN;  $\leq$ 5.0 x ULN if there is liver involvement by the tumor;
- Alkaline phosphatase  $\leq$ 2.5 x ULN ( $\leq$ 5 x ULN in case of bone metastasis).

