**Medical Conditions:**

1. All other forms of cancers not specified in Inclusion Criterion #3 unless currently considered cured (>5 years without evidence of recurrence).
2. Participants with known symptomatic brain metastases requiring steroids.  
Participants with asymptomatic or previously diagnosed brain metastases are eligible if they have completed their treatment and have recovered from the acute effects of radiation therapy or surgery prior to screening, have discontinued corticosteroid treatment for these metastases and are neurologically stable for at least 4 weeks (requires magnetic resonance imaging [MRI] confirmation) prior to randomization.
3. Planned radiation therapy as part of the primary anti-tumor therapy regimen.  
However, localized radiation therapy for symptomatic relief is permitted and if this becomes necessary after randomization, it will not be a reason for discontinuation.
4. Other acute or chronic medical or psychiatric condition including recent (within the past year) or active suicidal ideation or behavior or laboratory abnormality that may increase the risk associated with study participation or investigational product administration or may interfere with the interpretation of study results and, in the judgment of the investigator, would make the participant inappropriate for entry into this study.
5. Active hepatitis B virus (HBV) or hepatitis C virus (HCV).
6. Confirmed positive test for human immunodeficiency virus (HIV).
7. Current active reversible causes of decreased food intake, as determined by the Investigator. These causes may include, but are not limited to:

- National Cancer Institute (NCI) Common Terminology Criteria for Adverse Events (CTCAE) Grade 3 or 4 oral mucositis;
- NCI CTCAE Grade 3 or 4 Gastrointestinal (GI) disorders [nausea, vomiting, diarrhea, and constipation];
- mechanical obstructions making patient unable to eat.

8. Receiving tube feedings or parenteral nutrition (either total or partial) at the time of Screening.
9. Undergoing major surgery (central venous access placement and tumor biopsies are not considered major surgery) within 4 weeks prior to randomization. Patient must be well recovered from acute effects of surgery prior to screening. Patient should not have plans to undergo major surgical procedures during the study.
10. Severe gastrointestinal disease (including esophagitis, gastritis, malabsorption).
11. History of gastrectomy.

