### **6.1.1. Administration**

During all clinic visits, the dose of investigational product must be administered in the office by study personnel. PF-06946860 is to be administered first, followed by any premedications administered at the clinic (eg, antihistamine, anti-inflammatory agent, or pain reliever) and then the standard of care prescribed anti-tumor therapy. If the standard of care anti-tumor therapy is to be administered on the same day of dosing with PF-06946860, PF-06946860 will be the first drug administered during the clinic visit and must be given at least 0.5h prior to administration of the standard of care anti-tumor therapy. If the standard of care anti-tumor therapy is paused, adjusted or discontinued during the 12-week treatment period, this would not be considered a protocol deviation. PF-06946860 administration is to continue as prescribed by the protocol. The standard of care anti-tumor therapy may either be shorter or may continue beyond the study 12 week PF-06946860 treatment period according to the standard of care anti-tumor therapy for each cancer type and the treating physician's clinical judgment; this would not be considered a protocol deviation. Similarly, adjustments to the standard of care anti-tumor therapy dose or duration, including treatment holidays are at the discretion of the PI.

Premedication is permitted for all participants, consistent with institutional guidelines, and may include an antihistamine, anti-inflammatory agent, or pain reliever.

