#### **7.1.1. Criteria for Discontinuation**

Discontinuation of IP must occur for a participant meeting any of the following conditions:

- Criteria for a potential Hy's law case are met (see [Appendix 6](#)).
- Intent to become pregnant or pregnancy confirmed by serum beta human chorionic gonadotropin ( $\beta$ -hCG) testing.

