3.1.1. Adverse Events

An adverse event is considered a Treatment-Emergent Adverse Event (TEAE) if the event started during the effective duration of treatment. All events that start on or after the first dosing day and time/start time, if collected, but before the last dose plus the lag time will be flagged as TEAEs. The algorithm will not consider any events that started prior to the first dose date.

A 3-tier approach for summarizing AEs will not be used due to the low number of participants planned to be recruited.

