4. ANALYSIS SETS (POPULATIONS FOR ANALYSIS)

Data for all participants will be assessed to determine if participants meet the criteria for inclusion in each analysis population prior to unblinding and releasing the database and classifications will be documented per standard operating procedures.

Population	Description
Enrolled/Randomly assigned to investigational product	
“Enrolled” means a participant’s, or their legally authorized representative’s, agreement to participate in a clinical study following completion of the informed consent process.
 
Potential participants who are screened for the purpose of determining eligibility for the study, but do not participate in the study, are not considered enrolled, unless otherwise specified by the protocol

Evaluable	All participants randomly assigned to investigational product and who take at least 1 dose of investigational product
Safety	All participants randomly assigned to investigational product and who take at least 1 dose of investigational product
PK	All randomized participants who received a dose of PF-06946860 and in whom at least 1 serum concentration value is reported
PD	All randomized participants who received a dose of PF-06946860 and in whom at least 1 serum GDF-15 concentration is reported
Immunogenicity	All randomized participants who received a dose of PF-06946860 with at least 1 ADA result reported
Efficacy	All participants randomly assigned to investigational product and who take at least 1 dose of investigational product

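### Protocol 8.3.1.2 ends nonserious-AE recording at a loosely described new anticancer therapy, which can fall between IP doses, while other recording rules and the SAP's TEAE window and denominator run on

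*Protocol*

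**What the plan says.** Protocol 8.3.1.2 sets the cut-off: "If a participant begins a new anticancer therapy, the recording period for nonserious AEs ends at the time the new treatment is started". SAEs continue to be recorded. The only gloss on the term, in 8.3.1.1 and 8.3.1.2, is that moving to a commercial version of the study intervention counts, and that is limited to SAE reporting.

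Every participant receives separate anti-tumor therapy. Inclusion criterion 6 in Protocol 5.1 requires that they "Will be entering the study at the first or second cycle of their current course of anti-cancer treatment/therapy". Protocol 6.1.1 allows that therapy to be paused, adjusted or stopped during the 12 weeks and adds that "PF-06946860 administration is to continue as prescribed by the protocol". Protocol 7.1.1 opens its list of mandatory stops with "Discontinuation of IP must occur for a participant meeting any of the following conditions" and names only a potential Hy's law case and intended or confirmed pregnancy.

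SAP 3.1.1 runs the TEAE window from the first dose; events starting on or after it "but before the last dose plus the lag time will be flagged as TEAEs". The length of the lag is not given. The safety population in SAP 4 is "All participants randomly assigned to investigational product and who take at least 1 dose of investigational product", and SAP 6.1.1 summarizes AEs on that population. The incidence of TEAEs, serious and nonserious, is part of the primary endpoint (Protocol 3, SAP 3.1).

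**The concern.** The cut-off would suit a trial in which the study drug is itself the anticancer treatment. Here the IP is an anti-GDF-15 antibody for cachexia, given alongside anti-tumor therapy that may change on its own timetable. A change in that background therapy need not end exposure to the IP.

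If recording of nonserious AEs stops while doses of the IP are still being given, events from those doses can be missed. Injection-site reactions are the clearest case: Protocol 8.2 assesses them through ordinary AE monitoring, they are usually attributable to the IP, and many would be nonserious. The SAP would still count the participant as at risk to the end of the window and, with nothing recorded, as event-free. The error can only lower the nonserious part of the primary endpoint, in the first study of this antibody in patients with cancer and cachexia. Events never entered on the CRF cannot be recovered at analysis.

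**Working it through.** The plan states no figure to reproduce, so the check is a comparison of rules followed by an illustration of size.

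**1. When does recording of nonserious AEs end?**

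- Protocol 8.3.1.2, third paragraph: at the start of a new anticancer therapy.
- Protocol 8.3.1 and the first paragraph of 8.3.1.2: at the end of the active collection period, which runs at least to the final planned follow-up visit.
- SoA (Protocol 1.3): serious and nonserious AEs are monitored through follow-up, with no exception for new therapy.
- Protocol 8.2.5 (clinically relevant laboratory changes), 9.4.2 (examination findings) and the recording table in Appendix 3 (10.3.3): AEs go on the CRF, with no such cut-off.
- SAP 3.1.1, 4 and 6.1.1: TEAEs count to last dose plus lag over all dosed participants, with no truncation, flag or exposure adjustment.

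Only the first rule stops early, and the documents do not say which prevails.

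**2. Can the cut-off fall between doses?** Per the SoA, doses are on Days 1, 22, 43, 64 and 85. Protocol 6.5 leaves other necessary treatment to the treating physician, and 7.1.1 does not list a change of anti-tumor therapy. If the IP continues after a switch on Day 43, two doses (Days 64 and 85) remain.

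**3. How large could the effect be?** Assumptions: a nonserious event with true incidence *p* over the window, constant hazard, lag 0 (so the window is 85 − 1 = 84 days), switch on day *d* = 43, no recording afterwards, cohort of 8 with *s* switchers.

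- Recorded incidence in a switcher: rec = 1 − (1 − p)^((d − 1)/84), with (43 − 1)/84 = 0.5.
- Expected participants missed: s × (p − rec).
- Recorded cohort incidence: ((8 − s)p + s × rec)/8.

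| p | rec | Missed, s = 1 | Missed, s = 2 | Recorded incidence, s = 0 / 1 / 2 |
|---|---|---|---|---|
| 20% | 10.56% | 0.094 | 0.189 | 20.0% / 18.8% / 17.6% |
| 50% | 29.29% | 0.207 | 0.414 | 50.0% / 47.4% / 44.8% |

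The loss is 0.09 to 0.41 of a participant, or 0.094/8 = 1.2 to 0.414/8 = 5.2 percentage points. With s = 0 it is zero.

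**4. Sensitivity to the unstated lag.** If the lag were 84 days (to Day 169, an assumption), the exponent would be 42/168 = 0.25, with rec = 5.43% and 15.91%. The loss would be 0.146 (p = 20%, s = 1) to 0.682 (p = 50%, s = 2), where *p* is now the incidence over the longer window.

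**The case against.** The case for leaving the rule alone is that ending nonserious recording at a new regimen keeps out events caused by that regimen, in a small, uncontrolled, descriptive study with no hypotheses. SAEs are kept. So are AEs behind a stop in dosing: Protocol 8.3.1 says that if a participant permanently or "temporarily discontinues study intervention because of an AE or SAE, the AE or SAE must be recorded on the CRF". Safety data are reviewed monthly (Protocol 8.2). The points on what is kept stand. The attribution argument is weaker, because causality is assessed for every AE (Appendix 3) and SAP 6.1.1 already tabulates all-causality and treatment-related events separately.

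A reader might infer four stronger things that the documents do not support.

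- *Every nonserious event after a switch is lost.* The instructions without a cut-off listed under working could lead a site to keep recording. Loss follows only if 8.3.1.2 is applied literally.
- *A regimen switch during dosing is planned.* Pausing, adjusting or stopping therapy is not starting a new one. Dosing after a replacement regimen is permitted by silence, and 7.1 lets the investigator stop the IP for safety or tolerability.
- *Palliative radiation triggers the cut-off.* Exclusion criterion 3 says that "localized radiation therapy for symptomatic relief is permitted and if this becomes necessary after randomization, it will not be a reason for discontinuation". It contrasts this with radiation in the primary regimen, so symptom relief reads more naturally as supportive care under 6.5.
- *The share of the window lost is the bias.* After a Day 43 switch, 42/84 = 50% of the lag-0 window remains, but that is time in one switcher. Nor is the larger loss of up to 0.68 of a participant established: it needs an assumed 84-day lag or, at lag 0, switches by Day 22 (21/84 = 0.25, the same exponent). Day 22 precedes the earliest scheduled on-study CT (Day 43 − 14 = Day 29), so a switch prompted by progression on that scan would come later.

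The lag, or a rule for events after new therapy, may also sit in the sponsor reporting standards that the SAP cites but does not reproduce. Constant hazard may overstate the loss if AEs cluster early.

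**Conclusion.** The point holds as a conflict between stated rules that can understate nonserious TEAE incidence, not as a demonstrated loss of data. On the Day 43, lag-0 assumptions the effect is modest, well under one participant in 8. It depends on someone switching inside the window and on sites following 8.3.1.2 literally. The gap is confined to nonserious TEAEs; scheduled laboratory tests, vital signs and ECGs continue as data. It merits correction because it touches the primary endpoint, acts in one direction only, and cannot be repaired after the fact.

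**What to change.** Reconcile the passages:

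- Amend Protocol 8.3.1.2 so that nonserious AEs are recorded at least to the end of the SAP's TEAE window, whatever new anti-tumor therapy is started.
- State the length of the lag in SAP 3.1.1, so that the window has a defined end.
- In SAP 6.1.1, flag TEAEs that begin after a change of anti-tumor therapy so that they can be shown separately, and say what counts as a change relative to the course at entry.

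The cost is a protocol amendment with IRB/EC approval (Protocol 10.1.1), one sentence in SAP 3.1.1, and one derived flag with its definition. No new CRF field is needed: Protocol 6.5 already collects start and stop dates of concomitant treatments, and SAP 3.3.6 collects changes to anti-tumor treatment. The downside is some extra AE entries attributable to the new regimen, which the flag separates. If conduct is too far advanced for an amendment, the same dates can still identify participants whose recording may have ended early, and their number should be reported beside the TEAE tables.
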